# The Effect Of An Expanded Long Term Periodization Exercise Training In Patients With Cardiovascular Disease: Central And Peripheral Adaptations

## BACKGROUND

Cardiovascular Disease (CVD) remains the main cause of death in most European countries accounting for over four million deaths (47% of all deaths) each year. In Portugal CVD is among the main causes of morbidity, mortality and disability.

Cardiac Rehabilitation (CR) of patients with CVD has been practiced in Europe to varying degrees since the early 1970s. Coronary heart disease (CHD), if left untreated, is a progressive disease and individuals with CHD are at high risk for recurrent events. CR is a comprehensive, long-term program involving medical evaluation, prescribed exercise training (ET), cardiac risk factor modification, education and counselling. These programs are designed to limit the physiologic and psychological effects of cardiac illness, reduce the risk for sudden death or re-infarction, control cardiac symptoms, stabilize or reverse the atherosclerotic process, and enhance the psychosocial and vocational status of selected patients. Furthermore, it is a safe, useful and an effective treatment for patients with coronary artery disease (CAD), particularly after myocardial infarction (MI), but also for patients with cardiac interventions and chronic stable heart failure. Being a Class I recommendation from the American Heart Association, the American College of Cardiology, and the European Society of Cardiology, with exercise therapy consistently identified as a central element, guidelines recommend that patients with acute coronary syndromes should be offered comprehensive CR services in order to reduce risk factors that may have an impact on future cardiovascular complications.

Exercise adherence after a hospital-based CR program is reported to be poor with only 30% to 60% of those who complete a phase II CR program are still exercising 6 months later and after 12 months, up to 50 to 80% of participants failing to adhere to exercise. Despite the benefits associated with regular ET, adherence with supervised exercise-based CR remains low. More studies are needed to assess interventions that may help patients adhere to regular and effective ET after ending a hospital-based CR exercise program.

A brief review of meta-analysis studies that assess the impact of different types of exercise in short term outcomes for participants of CR will now be presented. The findings of a meta-analysis in 2015 indicated that high intensity interval training (HIIT) is more effective than moderate continuous training (MCT) for the improvement of both VO2 peak and the anaerobic threshold (AT) in patients with stable CAD. The greater improvement in VO2 peak following HIIT compared to MCT ( $4.6 \pm 3.1$  versus  $2.8 \pm 2.4$  ml/kg/min) is important in the context of a 10-25% survival advantage with every 3.5 ml/kg/min improvement in VO2 peak.

Another meta-analysis in 2016, compared HIIT and MCT in their ability to improve patients aerobic exercise capacity and various cardiovascular risk factors. Ten studies with 472 patients were included for analyses (218 HIIT, 254 MCT) and the main conclusions were that HIIT improves the mean VO2 peak in patients with CAD more than MCT, although MCT was associated with a more pronounced numerical decline in patients resting heart rate (HR) and body weight.

Current CR guidelines recommend the inclusion of a standardized resistance training (RT) program. A recent meta-analysis of ET programs in patients with CAD revealed that the addition of RT training to MCT led to superior improvements in body composition, muscle strength, peak work capacity, and a trend for greater

increases in VO2 peak. Similar to HIIT, RT has not been shown to compromise patient safety or program adherence.

Less is known about central and peripheral adaptations during long term effects on HIIT, MCT or even aerobic combined training with RT. In 2016, a systematic review and meta-analysis with a total of 63 studies with 14,486 participants with CHD median follow-up of 12 months were included. It was concluded that exercise-based CR reduces cardiovascular mortality and provides important data showing reductions in hospital admissions and improvements in quality of life. Madssen et al, showed that a 12-month maintenance exercise program consisting of infrequent supervised exercise sessions did not result in improved adherence to exercise or increased VO2 peak in CAD patients compared to usual care. One monthly session during a year of HIIT was not enough to improve or maintain exercise capacity. In the literature there is a lack of evidence on the effects in exercise capacity, muscle strength and body composition in long term weekly supervised exercise sessions on a maintenance exercise program in CVD patients.

Current exercise guidelines for CR focus on moderate intensity steady state exercises, with walking and cycling being the most recommended types of ET. The repetitive nature of this type of activity can become monotonous for the patient, affecting exercise adherence, compliance and training outcomes. Multiple training variables can be manipulated during exercise prescription, including repetitions, interval length, rest period length and intensity of resistance. In this regard, much insight could be gained from approaches used in sport conditioning, where exercise prescription is designed to be physiologically and psychologically sustainable using periodization.

Periodization was developed in the 1960's by the Russian physiologist Leo Matveyev and is defined as an organized cyclic program that uses planned variations in intensity, volume, and specificity to minimize fatigue and maximize performance outcomes. Periodized programs are composed of macrocycles, mesocycles and microcycles. The largest cycle or macrocycle is 1 year in length, each macrocycle is then broken into mesocycles, traditionally 1 to 3 months in length. Finally, each mesocycle is broken into individual microcycles. In healthy or trained populations, periodization aims to optimize ET adaptations as compared with non periodized training, to prevent overtraining and to avoid plateauing of training adaptations. The classical approach to periodization is linear periodized training, consisting in promoting wave-like progression, typically moving from general training (high volume/low intensity) towards specific training (low volume/high intensity). Periodized methods are considered to be superior to nonperiodized methods in trained populations and appears to be superior in inactive adults. Interestingly, a recent study investigated the effect of 22 weeks of 2 different types of periodization and 1 non periodization RT protocols on a comprehensive range of physical function and health outcomes in apparently healthy untrained older adults. Contrary of what was hypothesised, all three training models were equally effective for promoting significant improvements in various physical function and physiological health outcomes through RT in this population.

In most of the CR programs there are no periodization or exercise progression during medium to long term interventions. Further randomized controlled trials (RCT) are necessary to evaluate long-term periodization outcomes and assess the length of change observed in supervised CR programs.

## PURPOSE

To overcome the lack of knowledge regarding the physiological effects after hospital-based CR program, a 12 month RCT study will be performed. This study will hopefully contribute to generate evidence-based exercise prescription approaches to prolong the ET after the end of hospital-based CR programs.

The purpose of this research project is twofold:

1) To conduct a 12-month randomized control trial to evaluate the effects of periodized ET regime versus a non periodized ET regime on VO2 peak, maximal strength, body composition, functionality and quality of life in CVD patients.

2) to differentiate the effects of a 12-month periodized ET regime versus a non periodized ET regime on the different components of the oxygen kinetics response and oxidative adaptations in CVD patients.

The primary end points for aim 1 are: cardiopulmonary exercise testing (CPET) variables such as VO2 peak, AT, peak work rate, ventilatory equivalent of carbon dioxide (VE/VCO2), ventilatory equivalent of oxygen (VE/VO2), minute ventilation (VE), one repetition maximum (1RM), total body bone mineral content, lean and fat tissue mass and percentage of body fat mass, quality of life and functional physical fitness tests. The primary end points for aim 2 are oxygen kinetics and muscle deoxygenation dynamics of the vastus lateralis muscle at the submaximal test.

The hypothesis for this study are: 1) considering that this type of periodization exerts higher stress on the cardiovascular and neuromuscular systems, so that there could be greater adaptations, leading to higher increases in VO2max, muscle strength, body composition and functionality compared to non periodized ET regime; 2) there will be a better improvement microvascular O2 delivery in the exercise transient in response to periodized ET regime that would be associated with a faster adjustment of pulmonary VO2 kinetics than in non periodized group. Improvements in microvascular O2 delivery would be indicated by a better matching between the rate of adjustment of muscle deoxygenation relative to phase II pulmonary VO2, which represents a decreased reliance on O2 extraction for a given pulmonary VO2.

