## METHODS

### PARTICIPANTS

Patients with CVD that underwent to a hospital-based CR program in the Lisbon district Hospitals will be recruited. The study will be performed in the Cardiovascular Rehabilitation Center of the University of Lisbon (CRECUL) at the Lisbon University Stadium (EUL). The participants will be randomized into one of the following exercise groups: 1) periodized group; 2) non periodized group following the American College of Sports and Medicine (ACSM) guidelines. Patient's eligibility will be assessed according to the risk stratification criteria for patients with CVD for low and/or moderate risk stratification from the American Association of Cardiovascular and Pulmonary Rehabilitation. Male and female participants, ≥ 18 years of age, who had an established history of the following conditions or procedures will be included: MI, or coronary revascularization (coronary artery bypass grafting, percutaneous transluminal coronary angioplasty, or coronary artery stent), angina pectoris or coronary artery disease defined by angiography. Exclusion criteria

will be participants who had heart failure, heart transplants with either cardiac resynchronization therapy or implantable defibrillators; inability to comply with guidelines for participation in exercise testing and training; and significant limiting and/or unstable comorbidities that would prevent full participation.

Sample size was calculated (G-Power, *Version 3.1.3*) assuming a difference in peak oxygen uptake (VO2 peak) between groups of 3 ml/kg/min to be a clinically important difference with a SD of 3.5 ml/kg/min,  $\alpha=0.05$ ,  $1-\beta=0.80$  and an expected dropout rate of 37%. The calculations yielded a total minimum sample size of 50 participants (25 in each group).

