#### EXPECTED RESULTS

---

DXA provides descriptive data on the body composition of all patients from the studied groups and will be important to monitor the changes in body composition over time and to quantify the intervention effects particularly regarding fat free mass and muscle wasting. It will also allow adjustments to the expected differences between groups at the end of the study. It is not probable to find exercise-related changes in body weight but small reductions in percent total body and regional fat are desirable, as well as increases in lean soft tissue of the lower limbs in the exercise groups. The variables obtained in this task are primary endpoints of purpose 1 and secondary endpoints of purpose 2. We expect small reductions in regional fat layer thickness in the exercise groups, especially in periodized training group.

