## EXPECTED RESULTS

---

The variables measured in this task are primary end-points of purpose 1. We expect gradual improvements of the functional fitness test scores from M0 to M3 in both exercise groups, in particular the periodized training group.

---

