## EXPECTED RESULTS

---

The variables measured in this task are primary endpoints of aim 1. Significant improvements in maximal strength are possible as high from 50 and 69% of 1-RM among middle-aged CAD participants and over 80% of 1- RM in elderly CAD participants.

---

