### 13. STATISTICAL ANALYSIS

Data will be analyzed in M0, M1, M2 and M3. It will be tested the data for normality and homogeneity of variance with the Shapiro Wilk and Levene's tests, respectively. Data analysis will be described according to the established purposes for this project (descriptive values: mean, standard deviation, range, % change) and comparisons of means will be used for all purposed outcomes intra and inter groups. Baseline characteristics between groups will be evaluated with oneway ANOVA. Mixed between within subjects ANOVA will be conducted in a 2 (pre vs post ET) design to assess efficiency of the program. When a significant interaction is observed, t tests, or Wilcoxon signed-rank tests will be used to determine where the interaction occurred.

M0 versus M1, M0 versus M2, M0 versus M3, M1 versus M2, M2 versus M3 and M1 versus M3 will be compared to evaluate the changes in patients and trace the necessary timespan for such changes using General Linear Mixed Model Analysis for repeated measures with Tukey's posthoc procedure for the mean comparisons. Pearson product moment correlation coefficient or Spearman's rank correlation coefficient will be used to study the relationship between different variables by group and correlation coefficients will be compared between groups. Statistical significance will be set at an alpha level of 0.05. Other statistical procedures can be done.

Statistical analyses will be conducted using Statistical Package for the Social Sciences (SPSS) 22.0 (IBM SPSS Statistics, Chicago, IL, USA).

Data analysis will allow peer reviews redaction, slide presentations and oral communications in national and international conferences at the end of 2017 beginning of 2018.

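### Aim 1 has at least 13 primary endpoints (about 31 when expanded), all tested at 0.05 with no hierarchy, success rule or adjustment across them, although the trial is sized on VO2 peak alone

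*Combined protocol and SAP*

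**What the plan says.** The Purpose section introduces the aim 1 endpoints with "The primary end points for aim 1 are: cardiopulmonary exercise testing (CPET) variables such as" and then names six CPET variables, 1RM, four body-composition measures, quality of life and the functional fitness tests. The wording that introduces the CPET group leaves that group open-ended.

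The measurement sections repeat the primary label for whole groups of variables:

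- Section 4 (DXA), Expected Results: "The variables obtained in this task are primary endpoints of purpose 1 and secondary endpoints of purpose 2".
- Section 6 (functional fitness), Expected Results: "The variables measured in this task are primary end-points of purpose 1".
- Sections 8 (maximal strength) and 9 (SF-36), Expected Results, both: "The variables measured in this task are primary endpoints of aim 1".

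Section 13 (Statistical Analysis) says that "comparisons of means will be used for all purposed outcomes intra and inter groups" and that "Statistical significance will be set at an alpha level of 0.05". The only multiplicity procedure it names is Tukey's "posthoc procedure for the mean comparisons", which is attached to the pairwise comparisons among M0, M1, M2 and M3.

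The sample size under Participants was obtained "assuming a difference in peak oxygen uptake" of 3 ml/kg/min with an SD of 3.5. No other endpoint enters it.

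**The concern.** A primary endpoint is meant to settle whether an aim has been met. Here many variables carry that label, and the plan does not say which of them, or how many, must be significant. It therefore does not stop a single p<0.05 anywhere in the list from being presented as primary evidence for periodized training.

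The sample size calculation hints that VO2 peak leads, but no sentence gives it that role. Nor is a deciding visit fixed: the mixed ANOVA is described only as a before-and-after comparison, and there are three follow-up visits.

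At stake is the false-positive rate of the trial's main claim. Once the data have been seen, choosing the deciding endpoint is no longer credible.

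**Working it through.** **1. The plan's own figure.** Inputs from Participants: difference 3, SD 3.5, alpha 0.05, power 0.80, dropout 37%, total 50 (25 per arm). Standardised difference: 3/3.5 = 0.857. A one-sided t test needs 18 per arm, and 18 × 1.37 = 24.66, rounded up to 25, which reproduces the stated 50. A two-sided t test needs 23 per arm. Sidedness is not stated in the document. Either way the calculation covers one test of one variable, with no allowance for multiple primaries.

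**2. Counting the aim 1 primaries.**

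| Domain | As listed in Purpose | Expanded | Source of expansion |
|---|---|---|---|
| CPET | 6 | 6 | Purpose (open-ended) |
| 1RM | 1 | 6 | Section 8, six machines |
| DXA | 4 | 4 | Purpose |
| Quality of life | 1 | 10 | Section 9, 8 subscales + 2 summaries |
| Functional fitness | 1 | 5 | Section 6, five tests |
| Total | 13 | 31 | |

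**3. What section 13 controls.** Tukey adjusts visit pairs within one variable. The rule that follow-up tests are run after a significant interaction also works within one variable. Neither acts across variables.

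**4. False-positive chance.** Assumptions: one between-arm two-sided 0.05 test per variable, no true effects, and normal test statistics with a common correlation ρ. The documents give no correlations, so a range is shown. *Favouring periodization* means significant with the better result in that arm (2.5% for a single test).

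- Independent, favouring periodization: 1 − 0.975^13 = 0.280; 1 − 0.975^31 = 0.544.
- Independent, either direction: 1 − 0.95^13 = 0.487; 1 − 0.95^31 = 0.796.
- Correlated, favouring periodization: 1 − ∫ φ(u) Φ[(1.96 − √ρ·u)/√(1 − ρ)]^k du. For either direction, the bracketed probability is replaced by that of lying between −1.96 and 1.96.

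| | ρ = 0 | 0.3 | 0.5 | 0.7 |
|---|---|---|---|---|
| 13 items, favouring periodization | 28% | 21% | 17% | 12% |
| 31 variables, favouring periodization | 54% | 36% | 26% | 17% |
| 13 items, either direction | 49% | 42% | 33% | 24% |
| 31 variables, either direction | 80% | 67% | 51% | 34% |

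A block model is closer to the real structure: domains of 6, 6, 4, 10 and 5 variables, with assumed correlation 0.8 within and 0.3 between domains. Simulated with 400,000 draws, it gives 25% favouring periodization and 48% in either direction. At a common correlation of 0.9 the chance favouring periodization is 6.9% (13) or 8.7% (31), about three times nominal.

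**5. Power for VO2 peak.** Expected completers: 25 × 0.63 = 15.75, taken as 16 per arm. Two-sided t test, standardised difference 0.857:

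- alpha 0.05: 65%
- alpha 0.05/13 = 0.00385: 26%
- alpha 0.05/31 = 0.00161: 18%

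**The case against.** Several points can fairly be made for the plan.

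- **VO2 peak at 12 months is implied.** It comes first in the aim, the endpoint list and the hypothesis, it drives the sample size, and the aims and the CPET expected results refer to 12 months. This is a good reason to choose it, but the plan never fixes it, and section 13 also compares the 3- and 6-month visits.
- **The count of 31 is a matter of choice.** Using only the SF-36 subscales gives 29, and only its two summaries 23. Section 4 also describes regional mass, skeletal muscle index and waist, which could raise the count. Only *at least 13* is firm, and 13 is enough for the conclusion.
- **Not every variable has a predicted winner.** Hypothesis 1 omits quality of life. Dropping the ten SF-36 scores leaves 21 variables, and the chance favouring periodization becomes 41 / 29 / 22 / 15% at ρ = 0 / 0.3 / 0.5 / 0.7. That is lower, but still at least six times 2.5%.
- **Independence is unrealistic.** This is correct: fat mass and percentage fat come from the same scan. The zero-correlation figures are the upper end of the range, and the lower end still shows the problem.
- **Sidedness is not stated.** With a one-sided 0.05 test, VO2 peak power at 16 per arm is about 77% rather than 65%, and a mixed model may recover some information from partial follow-up. Neither reduces the multiplicity.
- **The study is small and physiological.** The document nevertheless calls these endpoints primary, states directional hypotheses and gives a formal sample size. If exploration is intended, it should say so.

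**Conclusion.** The concern holds. Aim 1 has at least 13 declared primaries in an open list, about 31 when the components are counted. All are compared at 0.05, with nothing that ranks them, defines success or adjusts across them. The chance of at least one false primary result favouring periodization is about 12% to 28% for 13 items and 17% to 54% for 31 variables, over assumed common correlations from 0.7 down to 0, against a nominal 2.5%. The block model puts it at about 25%.

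These figures rest on one two-sided between-arm test per variable and no true effects. They leave out the aim 2 primaries and testing at several visits, each of which adds further opportunities. The exact percentage depends on correlations that the documents do not give; the conclusion does not change at any value tried. This must be settled before any outcome data are analysed.

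**What to change.** Add one paragraph to the Purpose section and section 13:

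- Name the between-arm difference in VO2 peak at M3 (12 months) as the single primary endpoint for aim 1, tested at two-sided 0.05. This follows the sponsor's own sample size basis and 12-month aim.
- Make all other aim 1 variables secondary, and change the primary label in the Expected Results paragraphs accordingly. For these, either prespecify a multiplicity procedure over a short list chosen by the sponsor, or report estimates and confidence intervals with no confirmatory claim. A fixed sequence starting with VO2 peak would keep the full 0.05 for it and still allow later formal claims.
- For aim 2, name one oxygen-kinetic or deoxygenation parameter as the deciding endpoint, and state whether aim 2 is a separate primary family or secondary. That choice is the sponsor's.

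No new data are needed. The cost is that a significant result on another variable can no longer be presented as primary success, and aim 1 rests on a test with about 65% two-sided power at 16 completers per arm. That shortfall comes from the existing sample size and not from this change. Keeping all the primaries and splitting alpha by Bonferroni would cost more, leaving VO2 peak with about 26% power over 13 items or 18% over 31.

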### ***Submaximal exercise test***

On a separate day to the maximal test, patients will be recruited for a constant load exercise test. The test load is set at 80% of the value of the work rate corresponding to the AT detected in the maximum test, which was performed first, or 50% of VO2 peak, if the AT could not be adequately determined. Cardiopulmonary data will be recorded for 5 minutes at rest followed by 1 minute unloaded pedaling. After unloaded pedaling, patients will perform the constant load test for 6 min at the work rate described above, followed by unloaded pedaling for 5min. To improve the confidence of the kinetic parameter determination, this test will be performed three times and the averaged profile will be used for the kinetic analysis.

Curve fitting will be performed with Graphics software Origin version 7.0 (Microcal Software Inc., Northampton, Massachusetts, USA) using iterative techniques. The kinetics of the oxygen uptake response to the constant workload exercise will be analyzed by the sequent separate phases.

Before each maximal and submaximal test, the gas analyzer will be calibrated using ambient air and standard calibration gases of known concentration (16.7% O2 and 5.7% CO2). The calibration of the turbine flowmeter will be performed using a 3l syringe (Quinton Instruments, Seattle, Wash.) Twelve-lead ECGs, blood pressure, and ratings of perceived exertion will be recorded during each exercise stage.

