## EXPECTED RESULTS

---

The CPET will provide fundamental information to exercise intensity prescription and is a primary endpoint for purpose 1 and 2. We expect increases in VO2max in both training regimes from 5%–15% after 12 months of physical conditioning, with the greatest improvements in the periodized training group.

It is expected that there would be an improved microvascular O2 delivery in the exercise transient in response to both training groups that would be associated with a faster adjustment of VO2 kinetics, with the greatest improvements in the periodized training group.

---

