## 3. SKELETAL MUSCLE DEOXYGENATION DYNAMICS

The muscle deoxygenation dynamics of the Vastus Lateralis muscle will be evaluated throughout the submaximal CPET. Deoxyhaemoglobin [HHb], oxyhaemoglobin [HbO2], and total haemoglobin [HbT] concentrations will be quantified with a continuous-wave tissue oximeter (NIMO, Nirox srl, Brescia, Italy), based on the Near-infrared Spectroscopy (NIRS) system, which provides continuous, non-invasive monitoring of the relative concentration changes in these variables during rest and exercise. Briefly, this system is based on the oxygen dependency of absorption changes for near infra-red light in haemoglobin and myoglobin and it consists on an emission probe which emits three wave lengths (685, 850 and 905 nm) and a photon detector. The intensity of incident and transmitted light will be record continuously at 40 Hz and used to estimate the concentrations changes relative to baseline for oxygenated, deoxygenated and total haemoglobin. To account for the possible influence of the local fat layer on NIRS a real-time correction using an algorithm included in the software program v2.0 supplied with the spectrometer (Nimo Data Analysis Peak) will be used. Since the HHb signal is less dependent of changes in blood flow it can be used as an indicator of fractional O2 extraction within the microvascular level. This task will be performed at rest, during and immediately following the

submaximal CPET. The off- oxygen consumption and HHb kinetics will be determined using a monoexponential model which incorporates an amplitude, time constant and time delay.

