#### EXPECTED RESULTS

---

The off- oxygen consumption and HHb kinetics will be determined using a mono-exponential model which incorporates an amplitude, time constant and time delay. As the recovery of muscle and total body oxygenation from both maximal and submaximal exercise is delayed in sedentary participants, it is expected that the exercise training, in particular the periodized training group, induces a decrease of the time constant of the exponential decrease of these parameters.

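### Aim 2 names two families of fitted kinetic parameters as primary endpoints but no deciding parameter, transient or time point, and nothing controls error across them

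*Combined protocol and SAP*

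**What the plan says.** **Endpoint and objective (Purpose).** The aim 2 endpoint statement reads: "The primary end points for aim 2 are oxygen kinetics and muscle deoxygenation dynamics of the vastus lateralis muscle at the submaximal test". The objective is to separate the effects of the two regimes "on the different components of the oxygen kinetics response and oxidative adaptations in CVD patients". Neither sentence singles out a component.

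**Hypothesis 2 (Purpose).** It predicts faster adjustment of pulmonary VO2 during the exercise transient. It also says that better oxygen delivery "would be indicated by a better matching between the rate of adjustment of muscle deoxygenation relative to phase II pulmonary" VO2. No formula for this matching is given.

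**VO2 analysis (section 2, Submaximal exercise test).** The response to constant-load exercise "will be analyzed by the sequent separate phases". Fitting software is named, but no function or list of parameters.

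**Fitted model (section 3).** Off-transient VO2 and HHb kinetics use a "monoexponential model which incorporates an amplitude, time constant and time delay". The Expected Results that follow predict that training, especially periodized training, "induces a decrease of the time constant of the exponential decrease of these parameters".

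**Testing (section 13).** The plan states that "comparisons of means will be used for all purposed outcomes intra and inter groups", at an alpha of 0.05 with sidedness not stated. Follow-up tests after the mixed ANOVA depend on a significant interaction. Tukey's procedure is applied to the mean comparisons among M0, M1, M2 and M3.

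**The concern.** Aim 2 has its own hypothesis and its own primary endpoints, so naming a single primary for aim 1 would not settle it. The primary label is meant to carry weight: the Expected Results under section 4 classify the DXA variables as primary for purpose 1 but secondary for purpose 2.

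The quantity that is hypothesised (on-transient VO2 speed and its matching with HHb) has no stated model, and the quantity that is modelled (off-transient recovery) is not the one hypothesis 2 names. Suppose the off-transient HHb time constant shortened and phase II VO2 did not change. That would meet the expectation in section 3 and fail hypothesis 2, and the plan does not say which result decides. The choice would then be open after the data are seen, and a positive aim 2 claim would not carry the stated 5% error.

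**Working it through.** **The plan's own figures.** For aim 2 the only relevant figure is alpha = 0.05. No sample size or power is given for it. The total of 50 under Participants is calculated on VO2 peak (difference 3, SD 3.5 ml/kg/min). Of the variants tried, that total is reproduced by a one-sided t-test with dropout applied as a multiplier: 18 per arm × 1.37 = 24.7, rounded up to 25. It singles out no aim 2 parameter and is used below only for the number of completers.

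**Step 1. Count the candidate quantities.**
- Hypothesis 2 alone: on-transient VO2 adjustment and HHb/VO2 matching, so k = 2.
- Rate quantities in the hypotheses and expected results: on and off time constants for VO2 and HHb (2 × 2 = 4) plus matching, so k = 5.
- Off-transient model in section 3: 3 parameters × 2 signals, so k = 6.

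**Step 2. False-positive rate if any one is sufficient.** One between-arm comparison at one visit, each test two-sided at 0.05.

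Independent tests: 1 − 0.95^k.
- k = 2: 1 − 0.9025 = 0.0975
- k = 5: 1 − 0.7738 = 0.2262
- k = 6: 1 − 0.7351 = 0.2649

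Parameters fitted to the same curves are correlated. The documents give no correlation, so a common value ρ is assumed. Each statistic is Z = √ρ·C + √(1−ρ)·E, with C shared and E separate standard normals, and the rate is the probability that any |Z| exceeds 1.96.

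| k | ρ = 0 | ρ = 0.3 | ρ = 0.5 | ρ = 0.7 | ρ = 0.8 |
|---|---|---|---|---|---|
| 2 | 0.098 | 0.095 | 0.091 | 0.083 | 0.078 |
| 5 | 0.226 | 0.209 | 0.183 | 0.148 | 0.127 |
| 6 | 0.265 | 0.241 | 0.207 | 0.164 | 0.139 |

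Every cell exceeds 0.05. With one designated parameter the rate returns to 0.05.

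**Step 3. What the existing safeguards cover.** The interaction requirement and Tukey's procedure both act within a single outcome, across visits or groups. Neither acts across parameters, so neither changes the table.

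**Step 4. Power available to a corrected plan.** Completers per arm: 25 × (1 − 0.37) = 15.75, about 16. For 80% power, a two-sided two-sample t-test at 0.05 then needs a standardised difference of about 1.03. At 0.025, the first Holm step with two endpoints, it needs about 1.15. If the aim 2 effect were as large as that assumed for VO2 peak (3/3.5 = 0.857, an assumption here), power at 0.05 would be about 0.64.

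**The case against.** The strongest reply is that aim 2 is multi-component by design: it sets out to describe how components respond, and no power is claimed for it. The hypotheses also give a direction and speak of rates and time constants, not amplitudes or delays, which narrows the field. And the plan nowhere says that one positive parameter suffices. These points stand. They lower the plausible count from six to five or two and make the inflation conditional, but they do not supply a deciding quantity, and even two quantities exceed 5%.

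Three stronger readings are tempting and are not supported.

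- *The Expected Results under section 2 contradict the Purpose section.* They say that CPET "is a primary endpoint for purpose 1 and 2". Section 2 covers both the maximal and the submaximal test, so this fits the maximal test serving aim 1 and the submaximal test aim 2. The same text goes on to repeat hypothesis 2.
- *The candidates point in opposite directions.* Expecting faster recovery as well as faster onset is consistent. The example given above shows one result significant and another not, which is discordance and not reversal.
- *There are twelve parameters.* That requires a three-parameter on-transient model for both signals, which the documents do not state.

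**Conclusion.** The concern holds as a gap in specification with a measurable consequence. The aim 2 primary endpoints lack a named parameter, transient and time point; the stated model covers the off-transient while the hypothesis concerns the on-transient; matching is undefined; and no procedure controls error across the parameters.

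If one positive parameter were accepted as confirming aim 2, the false-positive rate would be about 8–10% (two quantities), 13–23% (five) or 14–26% (six), roughly 1.6 to 5.3 times the stated 5%. These figures rest on an assumed common correlation between 0 and 0.8, two-sided tests and a single visit. A reader might infer that the plan allows a claim on any parameter. It does not say so; that possibility follows only from the absence of a decision rule.

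This should be corrected before the aim 2 data are analysed. It does not affect the aim 1 endpoints.

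**What to change.** In the Purpose section and section 13, name one deciding contrast for aim 2: the between-arm difference in change from M0 to M3 in the phase II (on-transient) pulmonary VO2 time constant, tested two-sided at 0.05. Hypothesis 2 predicts its faster adjustment, M3 matches the 12-month aim, and the submaximal test already collects the data in three averaged repeats.

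Test the HHb/VO2 matching measure as key secondary, only if the primary is significant, and state its formula. If the sponsor prefers to keep both named endpoints at primary level, make these two quantities co-primaries with Holm adjustment.

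Label off-kinetics, amplitudes, delays and the M1 and M2 results as exploratory for aim 2. State the on-transient fitting model in the Submaximal exercise test part of section 2 and in section 3, including how phase II is delimited.

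**Cost.** No new data and no change to training or assessments, but the model and formula have to be written, not just relabelled. Off-kinetics and amplitudes can no longer be presented as primary findings. Under the hierarchy, the muscle deoxygenation outcome may go formally untested: at the assumed effect of 0.857 the primary would miss significance about 36% of the time (1 − 0.64). Holm avoids that dependence, but raises the difference needed for 80% power at its first step from about 1.03 to about 1.15 SD.
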